2.0 STUDY OVERVIEW

This open-label, multicenter, dose-ranging and expansion trial is designed to evaluate the safety and preliminary efficacy of intratumoral SD-101 in combination with pembrolizumab for the treatment of metastatic melanoma and HNSCC. The hypothesis to be tested in the clinical development of SD-101 is that SD-101, by virtue of its potency and its ability to induce high levels of interferons (IFNs), will have meaningful efficacy in generating anti-tumor immune responses when combined with an anti-PD-1 antibody. IFNs have multiple effects on both tumor cells and tumor-infiltrating leukocytes. These IFNs can directly inhibit the proliferation of tumor cells and increase MHC class I expression, enhancing antigen recognition. Additionally, IFNs have potent effects on tumor-infiltrating leukocytes, including enhancing the antigen presenting function of dendritic cells, increasing the effect or function of T cells, and activating cytotoxic activity of NK cells.

The rationale for treating metastatic melanoma and HNSCC with combination anti-PD-1/L1 therapy plus SD-101 is based on the unmet need to improve upon single anti-PD-1/L1 activity in these patient populations and nonclinical data (Protocol Sections 2.4 and 2.5) which suggest improved anti-tumor activity with the combination compared to anti-PD-1/L1 alone.

The study will be performed in 2 phases. The population to be studied in Phase 1 (Dose Escalation) will be patients with metastatic melanoma. The populations to be studied in Phase 2 (Dose Expansion) will be patients with metastatic melanoma and patients with

recurrent or metastatic HNSCC. In phase 1 of the study, doses of 1.0 mg, 2.0 mg, 4.0 mg, and 8.0 mg of SD-101 each in a single lesion will be tested in a modified, staggered, 3 + 3 trial design, to identify an optimal dose of SD-101 given in combination with pembrolizumab to be used in Phase 2 (see Protocol section 9.1 for DLT definitions and stopping rules). This optimal dose from Phase 1 is referred to in the protocol as the recommended Phase 2 dose (RP2D) of SD-101. Phase 2 of the study is designed to evaluate the safety and efficacy of SD-101 plus pembrolizumab in both metastatic melanoma and HNSCC patients. Tumor response will be evaluated separately for injected and non-injected lesions as well as all combined lesions in order to assess both a local and systemic response to study treatment.

The trial population includes a total of approximately 284 men and women with at least 1 site of disease that qualifies as a target lesion per RECIST v1.1 and is accessible for intratumoral injection.

Phase 1 Dose Escalation Cohorts 1-4 will include up to 24 patients with metastatic melanoma who are anti-PD-1 naïve or experienced.

Phase 2 Dose Expansion will include approximately 160 patients with metastatic melanoma and approximately 100 patients with recurrent or metastatic HNSCC:

- 1) Expansion Cohort 1 of approximately 60 melanoma patients who are anti-PD-1/L1 naïve
- 2) Expansion Cohort 2 of approximately 25 melanoma patients who have disease progression on anti-PD-1/L1 therapy
- 3) Expansion Cohort 3 of approximately 25 HNSCC patients who are anti-PD-1/L1 naïve
- 4) Expansion Cohort 4 of approximately 25 HNSCC patients who have disease progression on anti-PD-1/L1 therapy
- 5) Expansion Cohort 5 of approximately 25 melanoma patients who are anti-PD-1/L1 naïve
- 6) Expansion Cohort 6 of approximately 25 HNSCC patients who are anti-PD-1/L1 naïve
- 7) Expansion Cohort 7 of approximately 25 HNSCC patients who are refractory or resistant to anti-PD-1/L1 therapy
- 8) Expansion Cohort 8 of approximately 50 melanoma patients who are refractory or resistant to anti-PD-1/L1 therapy.

Some of these study groups will be rearranged for final analysis as analysis groups based on tumor indications, anti-PD-1/L1 experience, and dose of SD-101.

Phase 1 results will be presented for each of the 4 dose groups.

Results for Phase 2 objectives, using combined Phases 1 and 2 data, will be presented by 2mg/lesion and 8mg/lesion doses for

- MEL/NAIVE: metastatic melanoma patients who are anti-PD-1/L1 naïve, including
 - subjects in Phase 1 2mg and 8mg groups
 - subjects in Phase 2 Cohort 1 (both 2mg/lesion and 8mg single lesion) and Cohort 5 (2mg/lesion)
- MEL/EXP: metastatic melanoma patients who are anti-PD-1/L1 experienced, including
 - subjects in Phase 1 2mg and 8mg groups
 - subjects in Phase 2 Cohort 2 (both 2mg/lesion and 8mg/lesion) and Cohort 8 (2mg/lesion)
- HNSCC/NAIVE: HNSCC patients who are anti-PD-1/L1 naïve, including
 - subjects in Phase 2 Cohort 3 (both 2mg/lesion and 8mg/lesion) and Cohort 6 (2mg/lesion)
- HNSCC/EXP: HNSCC patients who are anti-PD-1/L1 experienced, including
 - subjects in Phase 2 Cohort 4 (both 2mg/lesion and 8mg/lesion) and Cohort 7 (2mg/lesion)

2.1 Phase 1

Patients in Escalation Cohorts 1-4 will be administered 1.0 mg, 2.0 mg, 4.0 mg, and 8.0 mg, respectively, of SD-101 in combination with 200 mg pembrolizumab Q3W per the Schedule of Trial Events (see Protocol Section 4.1.1 for dosing schema).

2.2 Phase 2

Melanoma Dose Expansion cohorts in Phase 2 will be treated with 8.0 mg or 2.0 mg of SD-101 from Phase 1 in combination with 200 mg pembrolizumab Q3W (see Protocol Section 4.1.2 for dosing schema).

HNSCC Dose Expansion cohorts in Phase 2 will be treated with the selected RP2D (8.0 mg or 2.0 mg of SD-101) from Phase 1 in combination with 200 mg pembrolizumab Q3W (see Protocol Section 4.1.2 for dosing schema).

3.0 STUDY OBJECTIVES

3.1 Phase 1 (Dose Escalation: Metastatic Melanoma)

3.1.1 Primary Objectives

- To assess the safety and tolerability of escalating intratumoral doses of SD-101 in combination with intravenous pembrolizumab in patients with metastatic melanoma
- To evaluate the expression of IFN-inducible genes in whole blood 24 hours after intratumoral injection of SD-101 given with pembrolizumab in patients with metastatic melanoma as a pharmacodynamic marker of SD-101 activity (pharmacodynamic)
- To determine a RP2D of SD-101 in combination with pembrolizumab to be evaluated in Phase 2

3.1.2 Exploratory Objectives

- To assess the preliminary response both locally and systemically including:
 - *Treatment response of the injected Lesion A (local response) (not implemented)*
 - *Treatment response of the non-injected lesion(s) (systemic response) (not implemented)*
 - Treatment response of all lesions
 - *Time to response (not implemented)*
 - To assess changes in tumor biomarkers (pharmacodynamic)

3.2 Phase 2 (Dose Expansion: Metastatic Melanoma or Recurrent or Metastatic Head and Neck Squamous Cell Carcinoma)

3.2.1 Primary Objectives

- To assess the tumor response both locally and systemically including:
 - Treatment response of the injected lesion(s) (local response)
 - Treatment response of the non-injected lesion(s) (systemic response)
 - Treatment response of all lesions

3.2.2 Secondary Objectives

- To assess the safety and tolerability of SD-101 in combination with pembrolizumab
- To assess the time frame of tumor responses:
 - Time to response
 - Duration of response
- To assess PFS

3.2.3 Exploratory Objectives

- To assess changes in tumor biomarkers

- To identify and assess changes in potential tumor neoantigens in patients with recurrent or metastatic HNSCC (pharmacodynamic)
- To evaluate the expression of IFN inducible genes in whole blood 24 hours after intratumoral injection of SD-101 given with pembrolizumab in patients with recurrent or metastatic HNSCC as a pharmacodynamic marker of SD-101 activity (pharmacodynamic)

4.0 ANALYSIS VARIABLES

Phase 1 – Dose Escalation

Primary Endpoints

- Incidence of DLTs
- Incidence of injection-site reactions, AEs, and SAEs
- Changes in the expression of IFN-inducible genes in whole blood (pharmacodynamic)

Exploratory Endpoints

- ORR per RECIST v1.1
- Changes in tumor-infiltrating lymphocytes, PD-L1 expression, and other gene expression in tumor biopsies (pharmacodynamic)

Phase 2 – Dose Expansion

The primary radiographic endpoints of the study will be based on RECIST v1.1 *and exploratory radiographic endpoints will be based on irRECIST (not implemented)*. All imaging endpoints for the overall response assessment will be based on investigator evaluation. A central imaging laboratory for study image collection and radiographic endpoint determination will be used per sponsor decision.

Primary Endpoints

- ORR per RECIST v1.1

Secondary Endpoints

- Incidence of injection-site reactions, AEs, and SAEs
- Time to response using RECIST v1.1
- Duration of response per RECIST v1.1
- PFS per RECIST v1.1

Exploratory Endpoints

- Changes in correlative biomarkers including tumor-infiltrating lymphocytes and PD-L1 expression at baseline and after SD-101 treatment (pharmacodynamic)
- Changes in potential tumor neoantigens in patients with recurrent or metastatic HNSCC (pharmacodynamic)

- Changes in the expression of IFN-inducible genes in whole blood in patients with metastatic HNSCC (pharmacodynamic)

5.0 SAMPLE SIZE CONSIDERATIONS

The Phase 1 trial is designed to allow preliminary assessments of safety, biological activity, and biomarkers in approximately 24 patients. Phase 2 of this trial is designed to allow preliminary assessments of efficacy, safety, and changes in biomarkers in approximately 210 patients. All analyses will be descriptive.

The Phase 1 trial sample size is based on a modified 3 + 3 dose-escalation trial design.

For the Phase 2 expansion cohorts, the sample sizes were determined based on power analysis of hypothesis tests and/or confidence intervals, although the efficacy analyses will be descriptive.

In Expansion Cohort 1, approximately 60 anti-PD-1/L1 naïve patients with metastatic melanoma will be enrolled. The null hypothesis that the response rate is < 35% will be tested against a 1-sided alternative at a significance level of 0.05. The design will provide greater than 90% power if the true response rate is > 55%. There will be no adjustments for multiplicity.

An exploratory sub-group analysis will be performed for those Expansion Cohort 1 subjects with PD-L1 negative tumors (ie, < 1% positivity) at baseline. It was estimated that this subgroup will have approximately 30 subjects. The analysis will have 80% power to reject the null hypothesis that the response rate is <15% with a one-sided test at a significance level of 0.05 when the true response rate is 35%. There will be no adjustments for multiplicity.

In Expansion Cohort 5, approximately 25 anti-PD-1/L1 naïve melanoma patients will be enrolled. This will allow preliminary estimate of the response rate associated with the dose and dosing schedule chosen for Expansion Cohort 5. If 14 or more responses are observed, the 95% exact confidence interval will yield a lower bound of no less than 37%.

In Expansion Cohort 2, approximately 25 metastatic melanoma patients who have disease progression on anti-PD-1/L1 therapy will be enrolled. The null hypothesis that the true response rate is 10% will be tested against a 1-sided alternative and will be rejected if 6 or more responses are observed. This design yields a type I error rate of 0.05 and 80% power when the true response rate is 30%. There will be no adjustments for multiplicity.

In Expansion Cohort 8, approximately 50 metastatic melanoma patients who are refractory or resistant to anti-PD-1/L1 therapy will be enrolled. If 13 or more responses are observed, the 95% exact confidence interval will yield a lower bound of no less than 15.0%.

In Expansion Cohort 3, approximately 25 anti-PD-1/L1 naïve HNSCC patients will be enrolled. The null hypothesis that the response rate is < 20% will be tested against a 1-sided

alternative at a significance level of 0.05. The design will provide greater than 80% power if the true response rate is $> 40\%$. There will be no adjustments for multiplicity.

In Expansion Cohort 6, approximately 25 anti-PD-1/L1 naïve HNSCC patients will be enrolled. This will allow a preliminary estimate of the response rate associated with the dose and dosing schedule chosen for Expansion Cohort 6. If 9 or more responses are observed, the 95% exact confidence interval will yield a lower bound of no less than 20%.

In Expansion Cohort 4, approximately 25 HNSCC patients who have disease progression on anti-PD-1/L1 therapy will be enrolled. The null hypothesis that the true response rate is 5% will be tested against a 1-sided alternative and will be rejected if 4 or more responses are observed. This design yields a type I error rate of 0.05 and 80% power when the true response rate is 21%. There will be no adjustments for multiplicity.

In Expansion Cohort 7, approximately 25 HNSCC patients who are refractory or resistant to anti-PD-1/L1 therapy will be enrolled. This will allow a preliminary estimate of the response rate associated with the dose and dosing schedule chosen for Expansion Cohort 7. If 4 or more responses are observed, the 95% exact confidence interval will yield a lower bound of no less than 5%.

Although changes to the groupings for the final analysis will be made, there is no impact to the sample size calculation, as all analyses will be descriptive. At some places in above sample size calculation one-sided significance level of 0.05 was referenced, to standardize the analyses, two-sided significance level of 0.05 is used throughout. Power and 95% exact confidence interval descriptions are still applicable if the underlying conditions in various analysis groups hold.

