In Expansion Cohort 2, approximately 25 metastatic melanoma patients who have disease progression on anti-PD-1/L1 therapy will be enrolled. The null hypothesis that the true response rate is 10% will be tested against a 1-sided alternative and will be rejected if 6 or more responses are observed. This design yields a type I error rate of 0.05 and 80% power when the true response rate is 30%. There will be no adjustments for multiplicity.

In Expansion Cohort 5, approximately 25 anti-PD-1/L1 naïve melanoma patients will be enrolled. This will allow preliminary estimate of the response rate associated with the dose and dosing schedule chosen for Expansion Cohort 5. If 14 or more responses are observed, the 95% exact confidence interval will yield a lower bound of no less than 37%.

In Expansion Cohort 8, approximately 50 metastatic melanoma patients who are refractory or resistant to anti-PD-1/L1 therapy will be enrolled. If 13 or more responses are observed, the 95% exact confidence interval will yield a lower bound of no less than 15.0%.

Sample size estimates for HNSCC expansion cohorts: In Expansion Cohort 3, approximately 25 anti-PD-1/L1 naïve patients will be enrolled. The null hypothesis that the response rate is < 20% will be tested against a 1-sided alternative at a significance level of 0.05. The design will provide greater than 80% power if the true response rate is > 40%. There will be no adjustments for multiplicity.

In Expansion Cohort 4, approximately 25 HNSCC patients who have disease progression on anti-PD-1/L1 therapy will be enrolled. The null hypothesis that the true

response rate is 5% will be tested against a 1-sided alternative and will be rejected if 4 or more responses are observed. This design yields a type I error rate of 0.05 and 80% power when the true response rate is 21%. There will be no adjustments for multiplicity.

In Expansion Cohort 6, approximately 25 anti-PD-1/L1 naïve HNSCC patients will be enrolled. This will allow preliminary estimate of the response rate associated with the dose and dosing schedule chosen for Expansion Cohort 6. If 9 or more responses are observed, the 95% exact confidence interval will yield a lower bound of no less than 20%.

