In Expansion Cohort 3, approximately 25 anti-PD-1/L1 naïve HNSCC patients will be enrolled. The null hypothesis that the response rate is $< 20\%$ will be tested against a 1-sided alternative at a significance level of 0.05. The design will provide greater than 80% power if the true response rate is $> 40\%$. There will be no adjustments for multiplicity.

In Expansion Cohort 4, approximately 25 HNSCC patients who have disease progression on anti-PD-1/L1 therapy will be enrolled. The null hypothesis that the true response rate is 5% will be tested against a 1-sided alternative and will be rejected if 4 or more responses are observed. This design yields a type I error rate of 0.05 and 80% power when the true response rate is 21%. There will be no adjustments for multiplicity.

In Expansion Cohort 6, approximately 25 anti-PD-1/L1 naïve HNSCC patients will be enrolled. This will allow preliminary estimate of the response rate associated with the dose and dosing schedule chosen for Expansion Cohort 6. If 9 or more responses are observed, the 95% exact confidence interval will yield a lower bound of no less than 20%.

In Expansion Cohort 7, approximately 25 patients who are refractory or resistant to anti-PD-1/L1 therapy will be enrolled. This will allow preliminary estimate of the response rate associated with the dose and dosing schedule chosen for Expansion Cohort 7. If 4 or more responses are observed, the 95% exact confidence interval will yield a lower bound of no less than 5%.

In Expansion Cohort 8, approximately 50 metastatic melanoma patients who are refractory or resistant to anti-PD-1/L1 therapy will be enrolled. If 13 or more responses are observed, the 95% exact confidence interval will yield a lower bound of no less than 15.0%.

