9.6.1 Objective Response Rate

The ORR is the proportion of patients who achieve a response of either CR or PR. ORR will be summarized and 95% Clopper Pearson confidence interval will be reported for each dose or analysis group.

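### Cohort 3 has 72.6% power, not more than 80%, and SAP 5.0 is wrong to say the power and exact-interval figures survive the move to two-sided 0.05

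*SAP*

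**What the plan says.** Protocol 12.2, the Protocol synopsis and SAP 5.0 give the same design figures for the Phase 2 expansion cohorts.

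- **Cohort 3** (about 25 patients, null rate 20%, one-sided 0.05): "The design will provide greater than 80% power if the true response rate is" above 40%.
- **Cohorts 1, 2, 4 and the PD-L1-negative subgroup of Cohort 1** have similar one-sided statements. Cohorts 2 and 4 also have printed rejection rules, of 6 and 4 responses in about 25 patients.
- **Cohort 5:** "If 14 or more responses are observed, the 95% exact confidence interval will yield a lower bound of no less than 37" per cent.
- **Cohort 6:** "If 9 or more responses are observed, the 95% exact confidence interval will yield a lower bound of no less than 20" per cent.
- **Cohort 7:** "If 4 or more responses are observed, the 95% exact confidence interval will yield a lower bound of no less than 5" per cent.
- **Cohort 8** (about 50 patients): 13 responses, with a lower bound of 15.0%.

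SAP 5.0 then says that, to standardize, "two-sided significance level of 0.05 is used throughout", and closes with "Power and 95% exact confidence interval descriptions are still applicable if the underlying conditions in various analysis groups hold". It gives no recalculated figure and names no two-sided test. For reporting, SAP 9.6.1 says "ORR will be summarized and 95% Clopper Pearson confidence interval will be reported for each dose or analysis group".

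Protocol 12.2 and SAP 5.0 put Phase 2 at about 210 patients. The Protocol synopsis, Protocol 4.1 and SAP 2.0 give about 160 melanoma plus 100 HNSCC patients.

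**The concern.** Moving from one-sided to two-sided 0.05 normally raises the rejection cutoff and lowers power, so a claim that nothing changes needs checking. So do the inherited figures themselves, because Cohort 3 claims more power for 20% against 40% than 25 patients would be expected to give.

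Objective response rate is the Phase 2 primary endpoint, and these sentences are the plan's only account of what each cohort size can show. A reader who applied the printed cutoffs or lower bounds would draw conclusions that the 95% Clopper-Pearson interval, calculated on the same counts, contradicts.

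**Working it through.** **Inputs** (SAP 5.0 and Protocol 12.2): sample size n, null rate p0 and alternative rate p1, as tabulated.

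**Power.** The cutoff r is the smallest count with P(X ≥ r | n, p0) ≤ α, where α is 0.05 one-sided or 0.025 in the upper tail for an equal-tailed two-sided test. Power is P(X ≥ r | n, p1).

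| Group | n | p0 / p1 | Stated power | One-sided 0.05: r, size, power | Equal-tailed two-sided 0.05: r, power |
|---|---|---|---|---|---|
| Cohort 1 | 60 | 35% / 55% | >90% | 28, 0.041, 92.3% | 29, 87.8% |
| PD-L1 negative | 30 | 15% / 35% | 80% | 9, 0.028, 77.5% | 10, 64.2% |
| Cohort 2 | 25 | 10% / 30% | 80% | 6, 0.033, 80.7% | 7, 65.9% |
| Cohort 3 | 25 | 20% / 40% | >80% | 9, 0.047, 72.6% | 10, 57.5% |
| Cohort 4 | 25 | 5% / 21% | 80% | 4, 0.034, 80.1% | 5, 62.7% |

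*Reproducing the plan.* At one-sided 0.05 the exact method recovers the stated power for Cohorts 1, 2 and 4, and the printed cutoffs for Cohorts 2 and 4. The printed type I error of 0.05 in those two is really the nominal level; the actual sizes are 0.033 and 0.034. The PD-L1 subgroup is 2.5 points short at exactly 30, but gives 81.8% at 28 patients (r = 8) and 81.1% at 31 (r = 9), so its one-sided figure is not disputed.

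*Cohort 3.* A cutoff of 8 would give 84.6% power, but its size is 0.109. No n from 20 to 34 reaches 80%: the best is 79.5% at n = 32 (r = 11), and the first to pass is n = 35 (r = 12, 80.5%). Normal approximations give 75.7% (null and alternative variances), 68.9% (continuity-corrected) and 71.4% (arcsine). Only a formula that uses the null variance under the alternative as well passes 80% (80.4%). With 25 patients, exact power passes 80% only between true rates of 42% (79.0%) and 43% (81.8%).

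*Dependence on the two-sided test.* The equal-tailed level is the one that matches a 95% Clopper-Pearson interval. Under it the printed rules for Cohorts 2 and 4 fail, since 0.033 and 0.034 exceed 0.025. Equivalently, the lower limits at 6/25 and 4/25 are 9.4% and 4.5%, which do not exclude 10% and 5%. Under a minimum-likelihood two-sided exact test, the p-values at the one-sided cutoffs are 0.077 (Cohort 1), 0.035 (PD-L1), 0.033 (Cohort 2), 0.074 (Cohort 3) and 0.034 (Cohort 4). Only Cohorts 1 and 3 then lose their cutoffs, again falling to 87.8% and 57.5%.

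**Interval bounds.** The Clopper-Pearson lower limit for x of n is the γ quantile of Beta(x, n − x + 1), with γ = 0.025 for a two-sided 95% interval and 0.05 for a one-sided limit.

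| Cohort | x / n | Stated | Two-sided 95% | One-sided 95% | Responses needed at this n | n at which stated x suffices |
|---|---|---|---|---|---|---|
| 5 | 14/25 | 37% | 34.9% | 37.9% | 15 | 23 |
| 6 | 9/25 | 20% | 18.0% | 20.2% | 10 | 22 |
| 7 | 4/25 | 5% | 4.5% | 5.7% | 5 | 22 |
| 8 | 13/50 | 15.0% | 14.6% | 16.1% | 14 | 48 |

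At the stated n, all four bounds hold only as one-sided 95% limits.

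**Phase 2 total.** Cohorts 1 to 7 give 60 + 6 × 25 = 210. Adding Cohort 8's 50 gives 260, which agrees with 160 + 100 and with the trial total, 24 + 260 = 284.

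**The case against.** The arithmetic is not contested; the case on the other side is about scope and weight.

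- **No test will be run.** Both documents say the analyses are descriptive, so two-sided power concerns tests nobody plans. True, and it limits the impact. But the SAP itself asserts that the power descriptions carry over, and that assertion is false.
- **The size of the loss depends on the test chosen.** This stands: under minimum likelihood the change of level newly breaks only Cohort 1, which would recover to 90.4% with 65 patients. Cohort 3 was already short. The sentence fails under either definition.
- **The interval errors do not come from the SAP's change of level.** Correct. The same bounds are in the Protocol, and an unqualified 95% exact interval is already two-sided. They need correcting whichever level is kept.
- **Sizes are approximate and some misses are small.** Cohorts 7 and 8 miss by about half a point or less, and 4.5% could be rounded to 5%. Cohorts 5 and 6 miss by about 2 points. The bounds are worded as minima, so small shortfalls still contradict them. Approximate n does not rescue Cohort 3.
- **Little can change now.** Enrollment is closed, Phase 2 efficacy collection has stopped, and the SAP regroups cohorts, so the printed per-cohort counts are not the denominators of the final tables. This argues for a wording correction and nothing more.

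**Conclusion.** The concern holds. Cohort 3's power is overstated by at least 7 points (72.6% against more than 80%) on the documents' own one-sided terms. The closing sentence of SAP 5.0 is wrong at two-sided 0.05 under both exact definitions examined. The lower bounds for Cohorts 5 to 8 are one-sided limits presented as 95% interval limits; the error is material for Cohorts 5 and 6 and minor for 7 and 8. The figure of 210 appears to omit Cohort 8.

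These results assume exact binomial calculation at the stated sizes and rates. The further falls in Cohorts 2 and 4 and the PD-L1 subgroup also assume the equal-tailed test. This is a correction to the stated design justification and does not threaten a planned decision, so it should be made but is not critical.

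**What to change.** 1. In the Protocol synopsis, Protocol 12.2 and SAP 5.0, restate Cohort 3 as about 73% power at a true rate of 40%, with rejection at 9 or more of 25 (size 0.047).
2. In SAP 5.0, either say that the power figures are one-sided 0.05 design figures, or remove the claim that they carry over and print the two-sided cutoffs and powers with the test named.
3. Under either option, restate the Cohort 5 to 8 lower bounds as 34.9%, 18.0%, 4.5% and 14.6% wherever they appear, including the Protocol.
4. Change 210 to 260 in Protocol 12.2 and SAP 5.0.

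The cost is wording only. The printed figures become less favourable; no patients, data or analyses are added.
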